7.3.3 Laboratory Parameters

Analysis visit will be applied for the laboratory parameter summaries.

Descriptive statistics for each laboratory parameter will be provided for scheduled visit and for the changes from Screening at each post-baseline visit. “Final” visit (Week 26 (Final)) will be defined as the last post-baseline available observation during the treatment period.

A shift table for the laboratory data at Screening versus Final will be constructed for laboratory parameters for which numeric reference ranges are available. The number of subjects below, within, and above the laboratory reference ranges at Screening versus Final will be summarized.

For each laboratory test, a complete data listing will be provided for subjects who have any laboratory results outside the reference ranges, and for subjects who have any laboratory results with clinical significance.

Plot of mean change from screening and spaghetti plot (all-subjects-in-one figure or selective individual subject figure) will be used to explore the trend of laboratory data change over the study, especially for serum albumin-adjusted calcium, urine calcium/creatinine ratio, phosphorus, PTH. Box-and-Whisker plots for PTH and Calcium/Creatinine ratio by visit will be constructed for data exploration.

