## 3 OVERALL CLINICAL TRIAL DESCRIPTION

This is an open-label, uncontrolled, multicenter long-term safety and efficacy study in pediatric subjects (age 2-16 years and 11 months, Version R03) with mild to moderate plaque psoriasis.

Approximately one hundred (100) subjects will be enrolled into this study. A subset of enrolled subjects (approximately 9 among the 100) will meet the PK requirements: pediatric subjects aged 2 to 6 years and 11 months (inclusive at Screening) and with a minimum 3% BSA involvement.

Qualified subjects will receive calcitriol 3 mcg/g ointment for a period of up to 26 weeks. The subject's parent/legal guardian or the subject under the responsibility of the parent/legal guardian will apply a thin film of study drug as needed to cover all involved areas twice daily, without exceeding a maximum of 0.5 g/kg of body weight or 28 g daily (whichever is the lower). If the subject experiences complete clearing of psoriasis per physician assessment (i.e. an IGA of 0), the subject should discontinue the study drug but continue to follow the visit schedule through the Week 26 visit. Treatment with study drug should be resumed if the IGA score is >0 and <4.

Subjects will be evaluated at screening, baseline and Weeks 4, 12, 26, and 30 as described in the Schedule of Assessments (Table 2). A visit window of  $\pm 5$  days will be allowed for Baseline and a visit window of  $\pm 3$  days will be allowed at the visits from Weeks 4 through 30.

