- The PTH returns to the normal reference range but falls below the lower limit of normal at any other stage during the course of the study

then the IDMC will be contacted for advice on management.

Subjects with abnormal serum albumin-adjusted calcium should temporarily discontinue study drug use immediately. The IDMC will be consulted for each occurrence of hypercalcemia, and depending on the severity and/or duration of the out-of-range serum calcium, will recommend appropriate management of the subject on a case-by-case basis in combination with other lab values and clinical condition of the subject in general.

Subjects with suspected kidney stones should temporarily discontinue study drug and will be referred to their Primary Care Physician (PCP) for care in tandem with Sponsor consultation of the IDMC. If urolithiasis is not confirmed, the subject may resume treatment with study drug. Subjects with confirmed urolithiasis should permanently discontinue study drug use and complete the Week 26/ET visit.

A subject who has been enrolled and assigned a kit number cannot be replaced by another subject if he/she discontinues the clinical trial for any reason.

For subjects not completing the entire study, all used (and unused) study drugs containers should be returned by the subject's parent/legal guardian to the defined personnel at the study center.

GALDERMA may also decide to prematurely terminate or suspend a subject's participation in the clinical trial.

Potential reasons for discontinuation, as listed on the Exit Form, are defined below:

- **Pregnancy:** **Withdraw the Subject from the clinical trial and follow the procedure described in Section 7.2.3.2.4**
- **Lack of Efficacy:** Investigator judgment only: based on therapeutic/disease-state expectations. If subject/parent or legal guardian opinion only, mark "subject request" and document it in the comment section of the eCRF Exit Form.
- **Adverse Event:** Complete an Adverse Event Form.
- **Subject Request:** Includes consent withdrawal, subject relocation, schedule conflicts. Explain the reason for withdrawal in the comment section of the eCRF Exit Form.
- **Protocol Violation:** Explain the violation in the comment section of the eCRF Exit Form.
- **Lost to Follow-up:** Confirmed with two documented phone calls and a certified letter (delivery receipt requested) without answer. Explain in the comment section of the eCRF Exit Form.

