### **6.3.4 Treatment compliance management and record**

Subjects / Subjects' parents/legal guardians will be required to fill out a dosing calendar to collect the date and time of each application and to bring back this dosing calendar at each visit. Upon study product return, the study staff will check the dosing calendar and the returned products. In case of bad compliance or missed applications, the study staff will re-instruct the subject / Subjects' parents/legal guardians on the proper use.

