### 9.1.5 Safety analysis methods

No inferential statistical analysis is planned for safety endpoints of the study.

The laboratory parameters at scheduled visits and change from Screening at post-baseline visit(s) will be summarized descriptively by treatment and by visit. A shift table for lab parameters at Screening versus Week 26/ET will be provided when appropriate.

Only Treatment-emergent Adverse Events (TEAEs) will be summarized. A TEAE is defined as an AE with an onset date on or after the first application of the study drug.

TEAEs will be tabulated in frequency tables by System Organ Class and Preferred Term based on the Medical Dictionary for Regulatory Activities (MedDRA). Additional summary tables will be provided for TEAEs that are considered serious (SAEs), related to the study drug(s), and severe. TEAEs that are AESIs, as well as TEAEs leading to discontinuation will also be summarized. For a given TEAE, a subject will be counted once even if he/she has experienced multiple episodes of that particular TEAE. Subgroup summaries of TEAEs will be provided based on gender, age group, and race when appropriate.

Prior and concomitant therapies and procedures will be summarized. A prior therapy/procedure is one that ends at or before baseline; and a concomitant therapy/procedure is one starting after the baseline visit.

Extent of study drug exposure and compliance will also be summarized.

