## **9.2 Sample size determination**

### **9.2.1 Assumptions**

No formal sample size calculation has been performed.

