### **9.2.2 Sample size calculation**

As a screen failure rate of approximately 40 percent is expected, screening of approximately 167 subjects is planned in order to achieve the target of 100 subjects enrolled into the study.

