7.5 Analysis Visit Definition

All efficacy variables, vital signs, and laboratory data will be summarized by analysis visit.

Analysis visit will be assigned according to the following algorithm to summarize the efficacy data by proper visit window interval. Study day is calculated as visit date minus the date of first application plus 1. Visit during treatment period will be used for analysis visits of Baseline to Week 26 assignment. Week 30 Follow-up will be the post-treatment/follow-up visit.

If multiple measurements are taken in the same interval, the one closest to the target study day will be used for the analysis. If two measurements are taken with equal differences in timing compared with the target date, the nominal visit number (recorded on the CRF page) will be used.

Table 2 Analysis Visit for Efficacy Data Summaries

Analysis Visit	Analysis Visit Number in Derived Dataset	Target Study Day	Visit Window for IGA, Pruritus, % BSA(Study Day)
Screening	-1	-	[< 1]
Baseline	1	1	[<= 1]
Week 4	2	29	[2 – 42]
Week 8	3	57	[43 – 70]
Week 12	4	85	[71 – 112]
Week 20	5	141	[113 – 161]
Week 26	6	183	[162- 196]
Week 26(LOCF)	6.999	-	Last available data during treatment period, including Baseline.
Week 30 Follow-up	7	-	Last available data during Follow-up data.

For efficacy data, screening visit will be assigned to analysis visit of screening as recorded on CRF page. If multiple measurements of screening due to rescreening or other unexpected reasons, the screening visit closest to date of first application will be chosen. If there is missing measurement at Baseline, Screening data will be used to impute the missing baseline data, if necessary, i.e. Baseline will be the last available data prior to first application. Only scheduled visit will be assigned into appropriate analysis visit; unscheduled visit will not be assigned to analysis visit, therefore, not in the summary.

When assigning the analysis visits for vital signs, no visit window will be applied; Nominal eCRF visit will be used as analysis visit for summaries.

When assigning the analysis visits for laboratory data, no visit window will be applied, however, the following rules will be applied:

1. If sample date/time is prior to date/time of first application, the data will be considered as screening visit. If multiple measurements of screening due to rescreening, retest or other unexpected reasons, the data closest to date of first application will be chosen.

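### Laboratory by-visit and Final values ignore whether drug was being applied, so the Screening-versus-Final shift table can show a drug-related excursion as normal after a laboratory-triggered stop

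*SAP*

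**What the plan says.** **Analysis side.** The key laboratory endpoints are albumin-adjusted calcium, urine calcium:creatinine ratio, phosphorus and PTH (Protocol 9.1.1.2, SAP 4.2). SAP 7.3.3 summarises change from Screening at each post-baseline visit and plans one shift table, Screening versus Final, with Final being "the last post-baseline available observation during the treatment period". SAP 7.5 states that "Visit during treatment period will be used for analysis visits of Baseline to Week 26 assignment". That sentence stands in the algorithm introduced for efficacy data. Laboratory data have their own rules lower in 7.5:

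- no visit window applies;
- samples before the first application count as Screening;
- scheduled samples are preferred;
- if the last scheduled visit in the treatment period has no laboratory data, the last subsequent unscheduled result becomes Final.

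The only dosing-related test in these rules is whether the sample precedes the first application.

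**Conduct side.** Protocol 5.6 says: "Subjects with abnormal serum albumin-adjusted calcium should temporarily discontinue study drug use immediately". The same section allows a temporary stop for PTH below the normal range, and Protocol 6.4 allows one for other out-of-range results. On complete clearing, "the subject should discontinue the study drug but continue to follow the visit schedule through the Week 26 visit" (Protocol 3). Protocol 7.2.2 has clinically relevant results repeated until they normalise or are explained. Parents or subjects must "fill out a dosing calendar to collect the date and time of each application" (Protocol 6.3.4).

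Everything is descriptive: "No inferential statistical analysis is planned for safety endpoints of the study" (Protocol 9.1.5).

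**The concern.** For calcium and PTH the endpoint can itself end exposure. A child whose calcium is high at Week 4 or 12 should come off drug. If the value then recovers, the later sample enters the Week 26 row and the Final column in the same way as that of a child who never stopped.

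High calcium, a high urine ratio and high PTH at Screening are exclusion criteria (Protocol 5.4). An eligible child whose calcium rises on drug and settles after the stop therefore appears in the only planned shift table as not high at Screening and not high at Final. There is no control arm against which a reader could notice this.

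The children at issue are those who matter most to a long-term safety question about calcium metabolism, and the table most likely to be read as the laboratory summary may not show them.

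**Working it through.** **1. The plan's own figures.** The only sample-size figure is the screening number ("As a screen failure rate of approximately 40 percent is expected, screening of approximately 167 subjects is planned", Protocol 9.2.2): 100 / (1 − 0.40) = 166.7, or 167. It reproduces, and this point does not depend on it. The adult hypercalcaemia rates in Protocol 1.3 also reproduce: 18/74 = 24.3% and 13/79 = 16.5%. They are used below for scale only.

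**2. Which outputs are touched.**

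- The Week 4 row (serum only) is largely free of the problem, because Week 4 is the first scheduled post-baseline blood draw and IGA.
- Week 12, Week 26 and Final can be affected. So can the Week 8 and Week 20 rows that the SAP still lists. Urine calcium:creatinine has no Week 4 sample, so all its on-study rows come after a possible stop.
- A value that triggers a stop was normally drawn before it. If drawn at a scheduled visit it stays in that visit's row, and if it is the Week 26 value it is Final. It leaves the shift table only when a later value replaces it.
- The SAP does not define the treatment period by dosing; its schedule uses the term for Baseline to Week 26/ET. If the term were read as first to last application, samples after a permanent stop would drop out, but samples taken during a temporary stop would remain.

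**3. Final shift table.** Suppose 24 of 100 children have an excursion (the adult rate, assumed) and a share r of them is back in range at Final for any reason. The count shown is 24 × (1 − r).

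| r | Shown at Final, per 100 | 95% exact interval |
|---|---|---|
| 0% | 24 | 16.0 to 33.6% |
| 25% | 18 | 11.0 to 26.9% |
| 50% | 12 | 6.4 to 20.0% |
| 75% | 6 | 2.2 to 12.6% |
| 100% | 0 | 0 to 3.6% |

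A worst post-baseline table shows 24 throughout. The documents do not give r.

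**4. Mean change at a visit.** Let f be the share of children off drug and q the share of the effect that persists off drug (both assumed). The mean shown, relative to all children on drug, is 1 − f(1 − q).

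| f | q = 0 | q = 0.5 | q = 1 |
|---|---|---|---|
| 5% | 95% | 97.5% | 100% |
| 10% | 90% | 95% | 100% |
| 20% | 80% | 90% | 100% |
| 30% | 70% | 85% | 100% |

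**5. Check of direction by simulation.** All settings are assumed: standardised calcium with between-child SD 0.8 and within-child SD 0.6, upper limit at 1.96, a uniform and fully reversible drug effect, draws at Weeks 4, 12 and 26, a stop after a value above the limit, and resumption after a value in range.

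| Effect (SD) | Week 12 mean change: plan / all on drug | Final above limit: plan / never stopped | Any post-baseline value above limit |
|---|---|---|---|
| 0.3 | 0.31 / 0.32 | 3.5% / 3.9% | 9.0% |
| 0.6 | 0.58 / 0.62 | 6.2% / 7.5% | 16.0% |
| 1.0 | 0.87 / 1.02 | 12.3% / 15.4% | 29.4% |

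From the unrounded output, the relative loss in the mean is 1 − 0.310/0.321 = 3%, 1 − 0.578/0.623 = 7% and 1 − 0.868/1.022 = 15%. In the Final rate it is 1 − 0.0351/0.0389 = 10%, 1 − 0.0624/0.0745 = 16% and 1 − 0.1225/0.1538 = 20%. The shift table loses more than the mean in each case. The last column is higher again, but much of that gap comes from looking three times instead of once, so it also carries random variation.

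**The case against.** **All-samples tables are legitimate.** The objective is the safety of up to 26 weeks of treatment under a regimen with built-in stops, and a summary of every scheduled value describes that regimen. This stands, and it is why the planned tables should stay. The SAP does not say that this is what they describe, and it offers no companion table.

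**The affected children are visible elsewhere.** The SAP plans complete listings for anyone with an out-of-range result, spaghetti plots of the key parameters, tables of calcium-related TEAEs and AESIs, and a summary of interruptions by reason and duration. The IDMC is alerted to hypercalcaemia and PTH changes. This also stands in large part. However, none of these outputs links a sample to exposure. Adverse event tables give partial cover, because an out-of-range value becomes an AE only if it suggests disease or toxicity or is judged pathological, and is new or worse (Protocol 7.2.2). Adult calcium rises were under 10% above the upper limit (Protocol 1.3), so similar rises might not qualify.

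**A reader might infer that the SAP passes off-drug values as on-treatment results and so biases the whole primary safety answer.** The documents do not support that. The SAP uses the period as its label and never calls the values on-treatment. Adverse events are a key safety endpoint in their own right, and the listings keep the triggering values.

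**A reader might also scale the bias from the adult excess.** That excess is 24.3 − 16.5 = 7.9 points (before rounding), with standard error √(0.243 × 0.757/74 + 0.165 × 0.835/79) = 0.065 and a 95% interval of about −4.9 to +20.6 points. It cannot be taken as an established drug effect, and the documents give no share of children off drug at any visit. Laboratory stops are described as temporary, so long off-drug spells before Final are possible but not the expected case.

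**Restricting to on-drug samples has its own bias.** By-visit rows limited to on-drug samples leave out the children stopped for abnormal values. This stands, and it shapes the fix.

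**Conclusion.** The point holds for specific laboratory tables. Values after Week 4 mix on-drug and off-drug samples, and some stops are caused by the laboratory value itself. If the effect reverses off drug, the Screening-versus-Final shift table is pulled toward no change; this is the main problem. The later mean changes are pulled the same way, by little when few children stop. If the effect persists off drug, the means are not diluted.

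The size cannot be derived from the documents. The run from 24 down to 0 per 100 is an illustration that rests on an adult rate and an assumed share back in range. The simulated losses (3 to 15% in means, 10 to 20% in Final rates) rest on assumed effects and full reversibility. No inferential result is affected, because none is planned. The change is worth making because it is cheap and uses data already collected.

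**What to change.** In SAP 7.3.3 and 7.5:

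1. Keep the planned all-samples tables and state that they describe values regardless of drug interruption. Define the treatment period for laboratory data explicitly.
2. Derive days since last application for each key laboratory sample from the dosing calendar, and flag the sample as on or off drug using a lag fixed in advance. SAP 7.3.1.3 already needs the days without application and the reasons, so dates should be in the database.
3. For calcium, urine calcium:creatinine, phosphorus and PTH, add two shift tables: Screening versus last on-drug value, and Screening versus worst post-baseline value (highest and lowest as relevant, unscheduled samples included). The second covers children whose excursion settles and who then resume.
4. List off-drug values with the reason for the stop.
5. Treat on-drug-only by-visit means as supportive only.

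**Cost:** one derived variable and a few tables. The worst-value table will look less favourable, partly through random variation, and a footnote should say so. No stopping rule changes. The SAP still describes 140 subjects and visits at Weeks 8 and 20, where the protocol plans about 100 and has removed those visits, so it needs revision in any case.

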7.3.1.3 Study Drug Exposure

The study drug is applied twice daily. Temporary drug discontinuations and dose modifications is permitted in instances of out-of-range laboratory results, local tolerability issues, and clearing/worsening of disease. Subjects also have missed doses due to other unexpected reasons. Reason for missed doses (either temporary drug discontinuations or dose modification), incidence of temporary drug discontinuation and dose modification, and corresponding duration will be summarized and examined.

Actual study drug exposure and expected study drug exposure will be calculated in two definitions (in days and in doses). Missed doses due to complete clearing of psoriasis (IGA=0) will be excluded from the expected exposure. Any other missed dose due to non-safety or safety reason, even protocol allowed, will not be deducted from the expected study drug exposure.

Actual study drug exposure in days = Treatment duration (days) – number of days with no applications in both PM and AM (temporary drug discontinuations).

Actual study drug exposure in doses = Treatment duration *2 – number of missed doses.

Expected study drug exposure in days = Treatment duration (days) – number of days with no applications due to complete clearing of psoriasis (IGA=0) only.

Expected study drug exposure in doses = Treatment duration * 2 – number of missed doses due to complete clearing of psoriasis (IGA=0) only.

Compliance will be based on actual study drug exposure versus expected study drug exposure. Compliance will be a good index of data integrity rather than protocol deviations

Compliance (%) in days = Actual study drug exposure in days /expected study drug exposure in days.

Compliance (%) in doses = Actual study drug exposure in doses /expected study drug exposure in doses.

Actual study drug exposure, expected study drug exposure, and compliance in two definitions (in days or in doses) will be summarized.

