2. Lab data from scheduled visit will be considered first when assigning analysis visit of each scheduled visit. If there is no data from scheduled visit available within the visit window, the last of those corresponding unscheduled visit will be considered for assignment of analysis visits.

3. When assigning Final visit, the lab data from the last post-baseline scheduled visit during treatment period will be considered first. If the last scheduled visit during treatment period have missing lab data due to any reason and there are subsequent unscheduled lab data available, the last of those corresponding unscheduled lab data will be assigned as Final visit. Otherwise, the previous visit lab data will be considered in the same manner.

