9 TABLE SHELLS AND REPORTING OUTPUT (GENERAL FEATURES)

The tentative list of tables to be produced in the reporting of this study is shown below. All eCRF data will also be available as subject listings and the eCRF data will be available in CDISC compliant data set. A separate document will be prepared for list of tables/figures/listing.

All summaries are based on Safety population.

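### For calcium, urine Ca:Cr, phosphorus and PTH the only specified reference-range count is Screening versus Final, so an earlier excursion that is back in range at the last scheduled on-treatment visit is tabulated as within range

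*SAP*

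**What the plan says.** Protocol 9.1.1.2 and SAP 4.2 name albumin-adjusted calcium, urine Ca:Cr, phosphorus and PTH, with adverse events, as the key safety endpoints.

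The reference-range tabulation is set out in two places:
- SAP 7.3.3: "The number of subjects below, within, and above the laboratory reference ranges at Screening versus Final will be summarized".
- Protocol 9.1.5: "A shift table for lab parameters at Screening versus Week 26/ET will be provided when appropriate".

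SAP 7.3.3 defines Final as the last available post-baseline observation on treatment. SAP 7.5, laboratory rule 3, says how it is chosen: "the lab data from the last post-baseline scheduled visit during treatment period will be considered first". Unscheduled results serve as Final only when the scheduled visit before them has no laboratory data. Rule 2 is similar for by-visit summaries: "If there is no data from scheduled visit available within the visit window, the last of those corresponding unscheduled visit will be considered".

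The laboratory items in SAP 9.3 are descriptive statistics with graphs, the shift table, listings of out-of-range and clinically significant results, and individual spaghetti plots for the key parameters. SAP 9 does not present this list as final: "The tentative list of tables to be produced in the reporting of this study is shown below", and "A separate document will be prepared for list of tables/figures/listing".

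Protocol 5.6 bears on how long an excursion may last. For calcium: "Subjects with abnormal serum albumin-adjusted calcium should temporarily discontinue study drug use immediately". For PTH below the lower limit, study drug may be interrupted and serum parameters are rechecked until PTH is normal again.

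**The concern.** In a long-term safety study, the laboratory question most readers will bring is how many children went out of range at any time on treatment. A last-value shift table answers a narrower question: how many were out of range at the end. The two answers differ most when an abnormal value leads to action that tends to bring it back to normal, and protocol 5.6 plans such action for calcium and, case by case, for PTH. The Final value then partly reflects what was done after the excursion.

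The Screening side of the table adds little for upward shifts. Protocol 5.4 (items 10, 11 and 22) excludes subjects above range at Screening for calcium, urine Ca:Cr and PTH, so for those three the table rests almost wholly on the single Final value.

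At stake is the tabulated on-treatment laboratory incidence for the primary objective. A reader who wants it would have to count subjects from listings or rely on adverse event reporting, which passes through investigator judgement.

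**Working it through.** The plan gives no figure on this point to reproduce. Its one sample-size figure does reproduce, 100/(1 − 0.40) = 166.7, rounded up to 167, but has no bearing here.

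**Step 1: apply the Final rule.** Take four subjects, all in range at Screening, on the protocol's serum schedule (Weeks 4, 12 and 26):

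| Subject | Week 4 | Week 12 | Week 26 | Later unscheduled retest | Final | Ever out of range |
|---|---|---|---|---|---|---|
| 1 | above | within | within | none | within | yes |
| 2 | within | above | within | none | within | yes |
| 3 | within | within | above | within | above | yes |
| 4 | within | within | within | none | within | no |

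The shift table shows 1 of 4 above range; 3 of 4 were above range at some time. Subject 3 stays above at Final because the scheduled result takes precedence over the retest.

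**Step 2: count on-treatment samples.** Serum pharmacodynamic samples: three in protocol Table 2 (Weeks 4, 12, 26) and five in SAP Table 1 (Weeks 4, 8, 12, 20, 26). Urine: two in both (Weeks 12 and 26). Both serum schedules occur in the trial, because protocol 10.5.2 keeps subjects already enrolled on the original protocol.

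**Step 3: bound the share missed.** Let w be the share of ever-abnormal subjects whose first excursion is at the Final sample, and r the share of the others whose Final value is still abnormal. Then

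share shown as within range at Final = (1 − w)(1 − r).

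- All onset at the Final sample (w = 1): 0%.
- Full persistence (r = 1): 0%.
- All onset earlier and all resolved (w = 0, r = 0): (1 − 0)(1 − 0) = 100%.

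**Step 4: illustrate under stated assumptions.** If onset is spread evenly over k samples, w = 1/k:

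| Samples k | r = 0 | r = 0.5 | r = 1 |
|---|---|---|---|
| 2 (urine) | 50% | 25% | 0% |
| 3 (serum, protocol) | 67% | 33% | 0% |
| 5 (serum, SAP) | 80% | 40% | 0% |

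Uneven onset moves these. With k = 3 and r = 0, an assumed onset split of 60/30/10 across the three samples gives 1 − 0.10 = 90%, and 10/30/60 gives 1 − 0.60 = 40%.

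A different assumption is a 5% chance of an abnormal value at each visit, independent between visits. Ever = 1 − 0.95^k, or 9.8, 14.3 and 22.6 per 100 subjects for k = 2, 3 and 5, against 5 per 100 at Final. The shares missed are 49%, 65% and 78%.

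None of these is an estimate for this trial. The available text gives no paediatric rate, onset pattern or persistence. Protocol 1.3 refers to adolescent PTH abnormalities described in Section 1, and that description is not in the text available for review.

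**The case against.** The strongest reply is that this is a matter of presentation. Every subject with any out-of-range result is listed, with individual plots for the key parameters (SAP 7.3.3 and 9.3). By-visit minimum and maximum are planned. Interruptions are summarized with their reasons: "incidence of temporary drug discontinuation and dose modification, and corresponding duration will be summarized and examined". Calcium-metabolism events and events of special interest are tabulated (SAP 7.3.2), and hypercalcemia and out-of-range PTH go to the IDMC as alerts (protocol 7.2.2.1). With about 100 subjects, an ever-count could be made from the listing. No inference depends on it, and no planned result is wrong.

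Most of that stands, and it limits the weight of the point. But none of these outputs is specified as a laboratory-based number and percentage. By-visit extremes do not count subjects, and they take unscheduled values only where no scheduled value exists. The interruption summary is not specified by laboratory parameter. Adverse event tables include an abnormal value only if the investigator judges it to suggest disease or toxicity or to be pathological, and new or worse since screening (protocol 7.2.2); the laboratory event of special interest also needs clinical significance and relatedness (protocol 7.2.3.1.3).

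A reader might infer more than the documents support, in four ways:
- That every resolved excursion disappears from the count. It does not: a Week 26 excursion that clears only on an unscheduled retest is still out of range at Final.
- That abnormal cases go undetected or unreported. The listings and alerts show otherwise.
- That most abnormal subjects will be missed. The bounds run from 0% to 100%, and the illustrations rest on assumed onset and persistence.
- That no such table will ever be produced. The separate table list (SAP 9) and the IDMC Charter (protocol 9.1.9) are not available here, so the finding is limited to the protocol and SAP.

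**Conclusion.** The point holds on the text of the two documents. For the four key laboratory parameters, the only specified count by reference range is a last-value comparison, and a subject out of range earlier but in range at the last scheduled on-treatment visit is counted as within range. The planned action on abnormal calcium and low PTH makes that pattern plausible. How often it will occur cannot be determined from the available text: the share of ever-abnormal subjects affected is 0% under full persistence or if all onset is at the Final sample, and 100% if all onset is earlier and all of it resolves.

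The gap is in the tabulated incidence, not in case detection or data collection. It is a cheap improvement: a count of any on-treatment abnormality describes laboratory safety better than the end-of-treatment shift alone. Confidence is high on the wording of the plan; the practical importance is unknown.

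**What to change.** In SAP 7.3.3 and 9.3, add one table for the four key parameters:
- Number and percentage of subjects with any on-treatment value below range and, separately, with any value above range. Counting each direction on its own avoids a single worst value, which can show only one direction.
- Denominator: subjects with at least one sample after first application, up to and including Week 26/ET.
- Exclude Week 30. Outside the PK group those samples are at the investigator's discretion (protocol Table 2) or taken only after an abnormal Week 26/ET result (SAP Table 1).
- Main column: scheduled samples only. Second column: scheduled plus unscheduled samples. Retests can raise an ever-count, so the two should be seen apart.
- For the three serum parameters, show both columns by visit schedule (three or five on-treatment samples). Urine needs no split because both schedules have two.
- Add a note that early terminators contribute fewer samples.

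Keep the Screening-versus-Final shift as the end-of-treatment table. If the separate table list already contains such a count, the SAP need only refer to it.

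The cost is SAP wording and one table from data already collected. Abnormality rates will look less favourable than in the Final shift, and with no comparator the count cannot separate drug effect from background. Protocol 1.3 shows why that caution belongs beside the table: in adults, hypercalcemia was seen in 16% (13/79) on vehicle against 24% (18/74) on calcitriol.
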